RESEARCH PROTOCOL

Home Goals: A randomised controlled trial to improve mental and physical health and well-being in young people

Short title of the study	Sponsorship and funding details
Home Goals	Sponsor organisation: Rotherham Doncaster and South Humber (RDaSH) NHS Trust Funders: RDaSH NHS Trust, Yorkshire Sport and Active Humber
Protocol version and date	Approval and registration details
(v2.1) 23/04/2021	Ethics approval reference: [TBC] Controlled trial registration: [TBC]

Clinical research team

[name]^{1,2}, [name]¹, [name]¹, [name]³, [name]^{1,2}, [name]⁴, [name]², [name]⁵, [name]², [name]², [name]², [name]⁶

- 1. Clinical Psychology Unit, Department of Psychology, University of Sheffield
- 2. Rotherham Doncaster and South Humber NHS Foundation Trust
- 3. Sheffield's Children's NHS Foundation Trust
- 4. Scunthorpe United Football Club
- 5. Bradford District Care NHS Foundation Trust
- 6. Bradford City FC

Charitable partners

[name]¹, [name]²

- 1. Yorkshire Sport
- 2. Active Humber

Chief investigator contacts details

[name]

RDaSH NHS Foundation Trust, [name]

Email: [contact]

Contents of the study protocol		Pg.
1.	Synopsis	2
2.	Background and rationale	3
3.	Objectives and hypotheses	4
4.	Study design	5
4.1	Setting and participants	5
4.2	Interventions	6
4.3	Measures	6
4.4	Recruitment, study procedures and data collection	8
5.	Statistical analysis plan	10
6.	Ethical considerations	11
7.	Risk management plan	11
8.	Dissemination plan	12
9.	References	13

1. Synopsis of the study		
Short study title	Home Goals	
ISRCTN registration no.	[TBC]	
Study Design	Multi-site randomised controlled trial	
Setting	School children attending schools across the geography of Rotherham Doncaster and South Humber (RDaSH) NHS Foundation Trust	
Study Participants	11-18 year olds who attend school in the RDaSH locality, who are at risk of, or are suffering from low-level mental health problems	
Aim	To evaluate if access to psychoeducation and physical activity intervention improves young people's health and wellbeing	
Objectives	 To assess changes in mental wellbeing To assess changes in physical wellbeing To assess completion and dropout rates 	
Primary outcome	Depression which is measured using the PHQ-9 modified for Adolescents (PHQ-A)	
Interventions	A 6-week, psychoeducation and physical education course consisting of online live psychoeducation sessions and physical activity sessions	
Randomization and data collection	Consenting participants will be randomly assigned to two groups; 1 and 2. Participants in both groups will be asked to complete outcome measures at an initial baseline assessment, after which only participants in group 1 will access a 6-week intervention (controlled phase). Next, group 2 will access the intervention during a 6-week period (full implementation phase). Finally, we will collect further outcome measures 6 months after both groups have completed the intervention (follow-up phase).	
Planned Sample Size	Minimum recruitment target of 192 participants, expecting 30% attrition.	
Data analysis method	 Trial data will be summarised using a CONSORT diagram and analyses will be based on intention-to-treat principles. The primary analysis will compare between and within-group differences in PHQ-A at baseline and 6 weeks, using ANOVA. Secondary analyses: between and within-group analyses will be conducted for GAD-7 and the physical activity measure at baseline and 6 weeks using ANOVA. Between-group and within-group effect sizes will be calculated using Cohen's d. Completion / dropout rates will be compared between groups using chi-square analysis. 	
Study Period	18 months (12 months active study period, plus 6 months analyses and dissemination)	

2. Background and rationale

Mental health problems cause huge public health burden in adolescents globally, as evidenced by a 20% prevalence (Belfer, 2008; World Health Organization (WHO), 2005). In the UK, the demand for Child and Adolescent Mental Health Services (CAMHS) services is at an all-time high and recent research shows children and young people referrals have increased by 26% in five years (Crenna-Jennigs & Hutchinson, 2018). Furthermore, 50% of children and young people that are assessed, wait more than 18 weeks to start treatment and over 3% wait over 12 months (Crenna-Jennings & Hutchinson, 2018).

For the treatment of depressive symptoms, existing literature reports the benefits of psychoeducation based interventions. Tursi, Baes, Camacho, Tofoli & Juruena (2013) concluded that psychoeducation is effective in improving the clinical course, treatment adherence, and psychosocial functioning of depressive patients. In a systematic review of 15 studies of psychoeducational interventions on depression conducted by Jones et al. (2018) it was ascertained psychoeducational interventions can have a role in preventing and managing adolescent depression as a first-line or adjunctive approach, however the limited number of studies, heterogeneity across formats and evaluation and inconsistent approach to defining a psychoeducational intervention, make it difficult to compare programmes and measure overall effectiveness.

Methods of administering the psychoeducational interventions have also been investigated; in a study looking at the effects of a Stress Control course with allied delivery by sports organisation (in this instance the Gaelic Athletic Association), Hayes et al. (2020) identified that participants who engaged with the intervention had identified positive lifestyle changes since completing the course, from generic self-care to making specific changes directed towards combating stress. Further, greater participation by participants (especially in male participants) was attributed to the delivery of intervention by sports professionals.

The WHO (2018) recommends that young people engage in at least one hour of moderate physical activity a day. In a recent publication by the Health Behavior in School-Aged Children (HBSC; Brooks, Klemera, Chester, Magnusson & Spencer, 2020) found that activity levels among young people are poor, with only 15% reporting being physically active of at least an hour a day, and in fact there has been a decline in physical activity reported by young people since 2002.

Research has demonstrated that physical activity may provide psychological benefits (Brown, Pearson, Braithwaite, Brown & Biddle, 2013; Dishman et al., 2006). Compared with traditional interventions, such as psychotherapy, psychosocial, and pharmacological interventions, physical activity has few side effects and is relatively cost-effective (Liu, Wu & Ming, 2015). Moreover, physical activity can be self-sustaining (Larun, Nordheim, Ekeland, Hagen & Heian, 2006), therefore reducing the need for future interventions. A growing literature suggests that physical activity can improve mental health (Hassmen, Koivula & Uutela, 2000; Penedo & Dahn, 2005), including depression, anxiety, self-esteem, anger, stress and so on (Alpert, Field, Goldstein & Perry, 1990; Babyak et al., 2000; Davis et al., 2011; Holley, Crone, Tyson & Lovell, 2011).

Recent research has demonstrated the importance of good physical health in maintaining good mental health for young people and adolescents (Biddle, Ciaccioni, Thomas & Vergeer, 2019). For example, vigorous physical activity has been shown to be a protective factor (OR = 0.78, 95%CI: 0.67–0.91) in urban adolescents (Piche, Huynh & Villatte, 2019). Physical activity has a huge potential to enhance our wellbeing. Even a short burst of 10 minutes' brisk walking increases our mental alertness, energy and positive mood. Physical activity plays an important role in children's cardiovascular health, abstract musculoskeletal health, mental and behavioural health, and physical, social, and cognitive development (Lobelo, Muth, Hanson & Nemeth, 2020).

Evidence suggests that physical activity improves depressive symptoms (Cooney et al., 2013; Nystrom, Neely, Hassmen & Carlbring, 2015), whilst decreased physical activity increases vulnerability to the development of depressive symptoms (Aberg, et al., 2012, Carroll, Blanck, Serdular & Brown, 2010;

Hamer, Molloy, de Oliveira & Demakakos, 2009). In two recent meta-analyses involving 40 and 38 studies respectively, it was found that physical activity was negatively associated with depressive symptoms (Korczak, Madigan & Colasanto, 2017; Liu et al., 2015).

A further meta-analysis of the use of physical activity to improve depression symptoms, found that the methodology is often problematic due to the low quality of the papers (Bailey, Hetrick, Rosenbaum, Purcell & Parker, 2018). However, physical activity was found to improve depressive symptoms in those aged 15-25 years. This paper highlights the need for stricter controls in studies, which this randomized control trial allows.

The combination of physical activity and psychoeducation in treatment of stress and depressive symptoms has shown to be superior than merely exercise alone. In a study looking at Dutch Women of low socio-economic status; exercise and psychoeducation compared with only exercise and a waiting list controlled condition (van der Waerdena, Hoefnagelsa, Hosman, Souren & Jansen, 2013) no indications were found that the exercise without psychoeducation reduced depressive symptoms and stress levels in the short or long term.

According to HSBC England National Report (Brooks et al., 2020) the most popular reasons for undertaking physical activity were to have fun and to improve health, therefore it seems logical to combine the most popular reasons to participate in physical activity with the significant findings of physical activity improving health and well-being adolescents to create an intervention that combines physical activity with psychoeducation to address depression and anxiety in adolescents.

This study is based upon the concept of Safety Nets which was developed as a face-to-face physical activity and psychoeducation intervention programme aimed at 11-18 year olds who are suffering from anxiety. The Safety Nets intervention was provided on site at either a football or rugby stadium. Both the psychoeducation and physical activity sessions lasted for an hour, and the physical activity sessions were taken by members of the local sports team/staff. However, due to the COVID-19 pandemic, the face-to-face sessions were no longer possible, therefore "Home Goals" was developed. Home Goals is an intervention that aims to ensure the safety of staff and participants by completing the sessions over video conferencing software. The team recognised that two hours may be too long for participants to engage when they are at home with a wealth of distractions, so the whole intervention time was halved.

The project aims to create therapy groups for children to improve their mental and emotional wellbeing. Each therapy group runs for one hour after school for six weeks, one half an hour focussing on physical activity (led by a local sports club) and another half an hour focusing on psychoeducation, led by NHS staff (e.g mental health nurse, psychiatrist, psychologist, Psychological Well-being Practitioners). The physical health aspect of the groups encompasses a broad range of physical activities, adapted to try at home. The groups also enable young people to learn about how and why anxiety and depression occur, and how we can learn ways of managing them.

This project is especially crucial given the nature of the COVID-19 pandemic, and ensuring the safety of staff and patients, by allowing the delivery of the interventions over video-conferencing software.

3. Objectives and Hypotheses

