3.1. Primary Objective

To assess changes in mental wellbeing

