3.3. Hypotheses

- A) Exposure to the intervention will be associated with significantly lower mean score of depression and anxiety by comparison to a waitlist (delayed intervention) control group
- **B)** After the control group is exposed to the intervention, there will be no significant differences in mean depression and anxiety level between the two groups (immediate intervention group, delayed intervention group)
- C) Mean depression and anxiety severity for all participants at the end of the 6-month follow-up period will be significantly lower than baseline severity (prior to intervention), but not significantly different to end-of-treatment severity, indicating maintenance of gains
- **D)** Attitude towards physical exercise will significantly improve following the intervention, and be maintained at the 6-month follow-up period.

4. Study design

This will be a pragmatic, stepped wedge, open-label, randomised controlled trial. Consenting participants will be randomly assigned to two groups, by a research assistant using a computerized randomization algorithm (applying a simple 1:1 randomization schedule). Participants will take part in one of the two 6-week interventions, depending on their group assignment. They will complete an online survey with standardised measures at baseline (prior to starting the interventions), after 6 weeks (after group 1 has finished and prior to group 2 commencing), after 12 weeks (post-treatment) and finally after 6 months (follow-up). All measures will be completed online using an industry-standard survey system which automatically sends email reminders to consenting participants.

The interventions will be delivered using an online approach; weekly online video-conference sessions involving half an hour of psychoeducation and half an hour of physical activity. Both interventions will involve a total of six 1-hour sessions delivered once per week using video-conferencing software that can involve large groups of participants. The study will be carried out in four phases, which are illustrated in Figure 1.

[figure not shown]

Figure 1. Trial design and measurement time-points

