5.2. Primary analysis

Trial data will be summarised using a CONSORT diagram and all analyses will be based on *intention-to-treat* principles. Missing data will be imputed using an expectation-maximization algorithm (Schafer & Olsden, 1998), prior to conducting formal analyses.

The primary hypothesis test (A) will be based on comparing mean outcome measures between groups at week 8, as shown in Figure 1. Mean PHQ-A scores will be compared between groups using analysis of covariance (ANCOVA), controlling for baseline severity.

Sensitivity analyses will be performed to assess the robustness of the main findings. This will involve repeating the above analysis including a random intercept for each trial site and additionally introducing "role" as a covariate (admin; mental health; other clinical role) and any other baseline demographics that may be unbalanced between groups.

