5.3. Secondary analyses

ANCOVA (and sensitivity analyses) described above will be repeated at each of the time-points illustrated in Figure 1 (weeks 0, 6, 12, 36), using the PHQ-A, and using the GAD-A as an outcome, controlling for baseline scores. Outcomes at 6-months follow-up (pooled for both groups) will be compared to outcomes at the baseline assessment, using paired-samples t-tests (or an appropriate non-parametric test depending on the distribution of the data).

These analyses will be repeated at each of the post-intervention time-points illustrated in Figure 1 (weeks 6, 36), using the WEMWBS sub-domain scores. These between and within-group comparisons will also be summarised using effect sizes (Cohen's d).

Post-intervention measures (weeks 6, 36) will be compared to baseline measures (week 0) within each group, using paired-samples t-tests or an appropriate non-parametric test depending on the distribution of the data. Within-sample pre-post treatment effect sizes will also be computed using the method proposed by Minami et al. (2008).

We will carry out an exploratory analysis of knowledge and levels of activity before and after the intervention.

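### The synopsis counts within-group PHQ-A change as part of the primary analysis, whereas the body of the protocol makes only the between-group comparison primary

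*Protocol*

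**What the plan says.** The synopsis (Data analysis method) states: "The primary analysis will compare between and within-group differences in PHQ-A at baseline and 6 weeks, using ANOVA". It does not say which of the two kinds of comparison decides the trial.

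The body of the protocol is narrower:

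- **Section 3.3, hypothesis A** predicts a "significantly lower mean score of depression and anxiety by comparison to a waitlist (delayed intervention) control group".
- **Section 5.1** sizes the trial for a between-groups ANOVA.
- **Section 5.2**, on the primary analysis, says: "The primary hypothesis test (A) will be based on comparing mean outcome measures between groups at week 8, as shown in Figure 1". It then gives the model: "Mean PHQ-A scores will be compared between groups using analysis of covariance (ANCOVA), controlling for baseline severity".
- **Section 5.3**, on the secondary analyses, holds the within-group tests: "Post-intervention measures (weeks 6, 36) will be compared to baseline measures (week 0) within each group, using paired-samples t-tests", or a non-parametric alternative.
- **Section 3.1** gives the primary objective as "To assess changes in mental wellbeing", with no comparator named.

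On timing, section 5.2 places the primary test at week 8. Section 5.3 has the analyses "repeated at each of the time-points illustrated in Figure 1 (weeks 0, 6, 12, 36", a list with no week 8. Section 4 puts the second assessment at six weeks, after group 1 has finished and before group 2 starts.

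**The concern.** The same family of tests is primary in the synopsis and secondary in section 5.3, and nothing in the protocol says which statement governs. The difference matters because the two kinds of comparison answer different questions. The between-group comparison at the end of the controlled phase is protected by randomisation. A pre-post change within group 1 mixes any intervention effect with whatever would have happened anyway.

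Some change without treatment is plausible here. Section 4.1 draws participants from CAMHS waiting lists, or from young people picked out by school staff as needing support with low mood, anxiety or stress. The delayed-intervention group exists to take natural improvement out of the estimate, and a within-group test gives that protection up.

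The fault is distinct from the two other mismatches between the synopsis and section 5.2 (ANOVA against ANCOVA, and week 6 against week 8). If only the model name and the week were corrected, the within-group element would still stand in the synopsis's definition of the primary analysis.

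**Working it through.** **1. The plan's own figure.** Section 5.1 gives 67 per group, 134 in total, for a moderate effect with 80% power and alpha 0.05. No numerical effect is stated; I take d = 0.5 and a two-sided test. The normal approximation gives n = 2(1.960 + 0.842)²/0.5² = 62.8, so 63 per group, and the t-test or two-group ANOVA gives 64. The stated 67 is slightly larger and has 81.9% power. The dropout step reproduces: 134/(1 − 0.30) = 191.4, so 192. The small gap between 64 and 67 has no bearing on this point. What matters is that the calculation is for a between-group test.

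**2. Inputs for the check.** From the protocol: n = 67 per group and alpha 0.05. Assumed, because the protocol gives neither: pre-post correlation r of 0.5 to 0.7, and a spontaneous fall δ of 0.2 or 0.3 SD, equal in both groups. The intervention effect is set to zero.

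**3. Formula.** The SD of a change score, in units of the PHQ-A SD, is √(2(1 − r)). The standardised change is δ/√(2(1 − r)), and the noncentrality of the paired t-test is that value times √n. The figures below are the probability of a significant *improvement* (upper tail of the noncentral t, two-sided 0.05).

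- Group 1, δ = 0.2, r = 0.5: 0.2/1.000 × √67 = 1.64, giving 36.4%.
- Group 1, δ = 0.2, r = 0.7: 0.2/0.775 × √67 = 2.11, giving 54.9%.
- Time effect pooled over both groups, δ = 0.2, r = 0.5: 0.2/1.000 × √134 = 2.32, giving 63.2%.

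| Spontaneous fall | Group 1 paired test (n = 67) | Pooled time effect, mixed ANOVA (n = 134) |
|---|---|---|
| 0.2 SD | 36–55% | 63–84% |
| 0.3 SD | 68–88% | 93–99% |

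**4. The randomised contrast.** A simulation of 20,000 trials per scenario at r = 0.6, with no intervention effect, compared change between groups. It rejected in 4.9–5.0% of trials at every fall tried from 0 to 0.5 SD. A common shift cancels in the between-group difference, so the baseline-adjusted ANCOVA behaves in the same way; simulated separately, it also stayed at about 5%.

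**5. If either result could be called primary.** In the simulation at r = 0.6, the chance that the between-group test or the group 1 test reached p < 0.05 was 8% with no fall, 46% at 0.2 SD and 79% at 0.3 SD.

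**The case against.** The strongest answer is that the body already settles the matter. Section 5.2 names one primary hypothesis test, section 5.3 makes the within-group tests secondary, section 5.1 sizes the trial between groups, and hypothesis A compares with the waitlist. This stands against the stronger reading that no single contrast decides the trial. A reader might infer that from the synopsis alone, but the protocol as a whole does not support it. What remains is a contradiction. Section 5.2 is not a clean authority either, since its week 8 is not a scheduled assessment.

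A second answer is that the synopsis may mean one mixed group-by-time ANOVA, with between and within naming the two factors. The interaction in that model compares change between arms and keeps its 5% error rate. The reading is fair, but the synopsis does not name the interaction as the deciding term, and the time effect of the same model is the pooled column in the table.

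A third tempting step is to count three primary tests, one between groups and one within each group. That gives about 62% and 90% for at least one significant result at 0.2 and 0.3 SD (r = 0.5). Those figures include change in the untreated waitlist group, which could not be presented as a success of the intervention, and no section specifies that set of tests. They should not be used.

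The size of any spontaneous fall is also unknown. Section 4.1 sets no PHQ-A entry threshold and excludes severe depression, so regression to the mean may be modest. This limits the precision of the figures but leaves the contradiction in place.

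**Conclusion.** The point holds as an internal contradiction about what is primary: the synopsis includes within-group PHQ-A change, and sections 3.3, 5.1, 5.2 and 5.3 do not. Under the synopsis wording, the chance that group 1's change would look like a positive primary result with no intervention effect is about 36–55% for a fall of 0.2 SD and 68–88% for 0.3 SD, against 5% for the between-group test. These figures rest on 67 analysed per group, two-sided 0.05, and the assumed correlations and falls.

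Two further inferences go too far. The within-group tests need not be dropped: hypothesis C is itself a comparison with baseline, and section 5.3 plans such tests as secondary, which is a legitimate place for them. Nor is the broad objective in section 3.1 an error, because the hypotheses in section 3.3 make it specific.

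**What to change.** In the synopsis, remove the within-group element from the primary-analysis sentence. State that the trial is decided by one contrast: the baseline-adjusted between-group difference in PHQ-A at the end of the controlled phase, analysed by ANCOVA as section 5.2 intends. The same edit settles the ANOVA/ANCOVA mismatch in that sentence. Reconcile week 8 in section 5.2 with the week 6 assessment used everywhere else.

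Keep the within-group comparisons of section 5.3 and hypothesis C as secondary analyses, and add a sentence saying that they do not establish efficacy against the waitlist. Rewording objective 3.1 as a difference between the immediate and delayed groups would help but is optional.

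The cost is an edit to the synopsis, one week number in section 5.2 and one sentence in section 5.3. No participants, data or power are lost. The protocol shows the trial registration as still to be confirmed, so the correction can be made before the primary analysis is registered.
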